C3.4. Urine metabolites of cannabis will be compared to neuroimaging and cognitive indices. From urine, we will assay 11 cannabinoids and metabolites including: THC, 11-hydroxy- Δ^9 -tetrahydrocannabinol (11OH-THC), 11-nor- Δ^9 -tetrahydrocannabinol-9-carboxylic acid (THC-COOH), 11-nor- Δ^9 -tetrahydrocannabinol-9-carboxylic acid glucuronide (THC-C-gluc), cannabinol (CBN), cannabidiol (CBD), cannabigerol (CBG), cannabidivarin (CBDV), Δ^9 -tetrahydrocannabivarin (THCV), and 11-nor-9-carboxy- Δ^9 -tetrahydrocannabivarin (THCV-COOH). *This study will be the first to compare urine cannabinoids and metabolites to neuropsychological performance and imaging measures of neuroinflammation (DBSI) in virally controlled PLWH and HIV- controls.* This is important because many studies only assess frequency of cannabis use, and it is now understood that potency, not just frequency, is an important indicator of exposure.⁸⁸

C3.5 Data-driven techniques will be applied to identify novel interactions. Prior studies of cannabis use and HIV have relied on traditional statistical methods that are generally insensitive to nonlinear models and high-order interactions believed to underlie complex clinical phenotypes. Our team has significant expertise in applying data driven techniques to discover novel mechanisms of changes in brain integrity within PLWH.^{89, 90} Biomarkers of peripheral and brain inflammation, detailed brain volumetrics, cognitive scores, demographics, and other relevant clinical data will be evaluated using data driven machine learning algorithms. *This study will be the first to use machine learning based feature selection methods to identify latent relationships and conditional dependencies seen with regular cannabis use and HIV status.* These methods are applicable for high dimensional data with binary or continuous outcomes, do not depend on heuristics, are noise-tolerant, and are sensitive to feature interactions and non-linear relationships, making them the optimal choice for the identification of novel biomarkers. Moreover, the methods proposed in this application will allow us to evaluate brain integrity without being biased by *a priori* regions of interest.

D Study Design

D1 Overview or Design Summary

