Once a person is deemed eligible, individuals will be given a more detailed description of the study including possible risks and benefits, either over the phone or in person. As part of the screening process, a medical record review may also be completed to fill in and confirm documented HIV+ status and length of time on cART and viral suppression (for PLWH); and presence of any medical condition or other criterion that would meet exclusion criteria or make it unsafe to participate in the study.

HIV negative healthy controls that are demographically matched as much as possible will be recruited from the friends, family and partners of their HIV+ counterparts, as well as from various community organizations as described above.

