Serious adverse events may be reported to the IRB within the timeline outlined in their policies and procedures. The stopping criteria and guidelines to be used for this protocol may include the following: 1) The study may be stopped if there is clear evidence of harm or harmful side effects of the procedures used in this protocol; 2) In the event that a serious adverse event (SAE) occurs that increases the risks to participants, the study may be stopped and an investigation be conducted and a findings report generated by the PI; 3) Should there be an SAE or adverse event (AE) that occurs at a frequency greater than 5%, it will be added to the consent document, if not already addressed, and enrollment may be halted while a determination is made regarding the potential risks to participants. The risks of the study are low, however, the PI and study physicians as well as the WUSTL IRB will review safety material and the protocol at least annually.

F Statistical Plan

Considerations for data science methods: Continuous variables will be transformed as needed prior to analyses to improve normality and linearity of the relationship to the designated outcome variable. Raw NP tests that measure time on a task will use an inverse transformation $f(t) = 1/t$, measuring the speed of task completion; for other tests an empirical normal quantile transformation and normative corrections for demographics will be considered, which will lead to scale scores and z-scores. NP global and sub-domain values are likely to be normally distributed, which will allow for multivariable linear regression. The distributions of depression, apathy, and HRQoL scores are likely to be right-skewed and over-dispersed; therefore, negative binomial regression may be considered for analyses. All statistical tests will be two-sided, with significance declared at the $p < 0.05$ level (unless otherwise stated). In addition to hypothesis testing, 95% confidence intervals (95%CI) will be determined for effect sizes of interest. Sex will be investigated as a potential predictor of interest for each hypothesis and analysis. In exploratory analyses, correction for multiple comparisons will preserve the false discovery rate (FDR) at the 0.05 level.

Demographics: Demographic, medical, psychosocial, and lab characteristics of participants will be summarized using N (%) for categorical variables, and mean, standard deviation, and range for numeric variables.

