Hypothesis 2b: The effect of THC and CBD concentrations among cannabis users on NP and brain volumetrics will be analyzed using linear models. Demographic factors such as the WRAT-4, sex, and age will be examined as explanatory variables and will be incorporated into the final models if significant at $p<0.20$ in backward model selection. Possible non-linear cannabis effects will be explored, including quadratic effects and smooth effects fitted via generalized additive models. A possible interaction between cannabis exposure levels and HIV will also be examined.

Hypothesis 2c: Data-driven feature selection methods⁹²⁻⁹⁵ will be performed to reveal highly dimensional mechanisms and associations between cannabis use and brain integrity (cognition and volumetrics) that differentiate HIV serostatus from regular cannabis use. The analysis will yield a subset of biomarkers that are most indicative of the effects of cannabis on brain integrity (NP and volumetrics), while excluding irrelevant and redundant biomarkers. Continuous variables will be normalized to zero mean and unit variance. Features will be scaled independently to a common interval to ensure that features with higher magnitudes are not given preference during training. All analysis will be conducted with 10-fold cross validation with 10 repeats to ensure the reliability of the results.⁹⁶ Individual models will be trained with a categorical cross entropy loss function, and evaluated based on sensitivity, specificity, and receiver operator curve (ROC) area under the curve (AUC) F1 analyses. Models will be compared using the mean misclassification rate and Bayesian information criteria.⁹⁷ All analysis will be performed in common programming languages and packages (MATLAB, Python, and R).

Power Analysis for Aim 2:

Hypothesis 2a: With the proposed sample size of $n=320$ we have $\geq 80\%$ statistical power to detect additive effects of HIV status and cannabis use on NP and volumetrics outcomes corresponding to Cohen's $d=0.314$ each. This effect size is consistent with those determined in our preliminary data (Cohen's $d=0.584$ for cannabis and $d=0.418$ for HIV in *Figure 5*).

Hypothesis 2b: We have $\geq 80\%$ power to detect an effect of cannabis exposure among cannabis users on NP or volumetric outcomes corresponding to $R^2=0.047$ proportion of variance explained, or equivalently

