a Pearson correlation coefficient of 0.219. For comparison, in our preliminary analyses we found $r=0.23$ (Figure 3B).

Hypothesis 2c: Sample size determination for classifier development aims will seek to improve predictor accuracy and significance.⁹⁸ Sample size determinants will be conducted using proposed published methods. Training and testing errors of cross validated progressively sampled models will be assumed to follow power laws and will be evaluated based on asymptotic error value convergence to identify appropriate sample sizes.^{99, 100} Results will be optimized based on nonlinear weighted least squares fitting.¹⁰¹ Cross validated model performance will be compared using empirical and uniform priors to determine the effect of balanced classes.¹⁰² Cross validation of data with randomly permuted labels will be used to identify the significance of model results.¹⁰³

G Data Handling and Record Keeping

1. Confidentiality and Security

All data will be safeguarded in accordance with HIPAA and the principles and practices of strict confidentiality. Studies are done for research purposes only. The risks of breaching confidentiality will be rigorously limited by the use of locked and restricted access to data. No identifiers will be included in any reports generated by this study. All key personnel involved in the design or conduct of research that involves contact with human subjects will receive the required education on the protection of human research subjects prior to beginning work on this project. All electronic data transferred to Drs. [name] [name], or [name] will be de-identified and sent via encrypted email, encrypted hard drive by courier, or by providing them access to a secure database (i.e. RedCap, CNDA, WUSTL Box, etc.). All biological data sent to Temple University will be done via courier.

2. Training

All study staff must complete CITI and HIPAA training and be listed as engaged with the IRB before they will be able to perform any study procedures. Study staff must also review protocol and sign a delegation log expressing understanding and commitment to adhere to it.

3. Case Report Forms and Source Documents

Copies of participants' medical records containing data to be used in the study (i.e. lab values, diagnoses, lists of medication, etc.) should be placed in the file whenever possible. Should these source documents not be available, subject report is acceptable.

4. Records Retention

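### Hypotheses 1c and 2c do not specify how age, sex and WRAT-4 are handled, and cannabis users and non-users are not stated to be matched, so demographic differences can be reported as cannabis biomarkers

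*Combined protocol and SAP*

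**What the plan says.** - **Pipeline.** Section F gives the same pipeline for 1c and 2c: "Continuous variables will be normalized to zero mean and unit variance", then range scaling, 10-fold cross-validation with 10 repeats, a cross-entropy loss, and comparison of models by misclassification and BIC. It names no covariate adjustment, residualising, head-size correction or demographics-only comparator.
- **Output.** For 2c: "The analysis will yield a subset of biomarkers that are most indicative of the effects of cannabis on brain integrity (NP and volumetrics". The 1c text makes the same kind of statement for immune activation and inflammation.
- **Inputs.** C3.5 states: "detailed brain volumetrics, cognitive scores, demographics, and other relevant clinical data will be evaluated using data driven machine learning algorithms". It does not require biomarkers to be selected conditional on the demographics.
- **General provisions.** The opening paragraph of section F lists demographic normative correction as something to consider, for tests not scored by time. It also says that sex will be looked at in every hypothesis and analysis.
- **Contrast with the linear models.** Hypotheses 1a, 1b and 2b examine WRAT-4, sex and age by backward selection at p<0.20. Hypothesis 2a adjusts for confounders.
- **Matching.** D3.1 refers to "HIV negative healthy controls that are demographically matched as much as possible", and D1 describes similarity in the same sense, by HIV status. Nothing is stated for users against non-users. Ages run from 18 to 70 (D2.1).
- **Significance.** Under the power sections for 1c and 2c: "Cross validation of data with randomly permuted labels will be used to identify the significance of model results".

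**The concern.** Cannabis use is not randomised, and users may differ in age, sex or education from non-users. D3.1 includes flyers at dispensaries, which could bring users in through a different channel. If brain volumes, test scores or immune markers vary with age or sex over an 18-70 range, a classifier can separate users from non-users by recovering demographics from the features.

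Neither planned safeguard would show this. Cross-validation does not, because the same imbalance sits in every fold. Permuting labels does not, because it breaks the link between age and cannabis together with any true cannabis effect. It tests for any association, not for one beyond demographics. At stake is the meaning of the main product of 1c and 2c, a list of biomarkers described as showing what cannabis does.

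**Working it through.** **1. The plan's own figure.** The documents give no numerical power or sample size for 1c or 2c. The nearest figure is for Hypothesis 2a: at n=320, at least 80% power for "additive effects of HIV status and cannabis use on NP and volumetrics outcomes corresponding to Cohen's $d=0.314$ each". The test is two-sided at 0.05. With 160 users and 160 non-users:

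Power = Φ(d√(n/2) − 1.96) = Φ(0.314 × √80 − 1.96) = Φ(2.81 − 1.96) = 80.2%.

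The noncentral t gives 80.0%. The figure reproduces, and nothing below disputes it. It sets the sample and the scale.

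**2. Assumptions.** The documents give neither an age gap between users and non-users nor an age-feature correlation. I take a gap δ of 0.2-0.5 SD and a correlation ρ of 0.3-0.6, for features with no cannabis effect. The check treats the problem as two classes, users against non-users.

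**3. One feature.** An unadjusted feature shows a spurious standardised difference of ρδ. With 160 per group, the chance of p<0.05 follows from the formula in step 1 (plus the negligible opposite tail):

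| δ | ρ | ρδ | P(p<0.05) |
|---|---|---|---|
| 0.2 | 0.3 | 0.06 | 0.08 |
| 0.3 | 0.5 | 0.15 | 0.27 |
| 0.5 | 0.3 | 0.15 | 0.27 |
| 0.5 | 0.5 | 0.25 | 0.61 |
| 0.5 | 0.6 | 0.30 | 0.77 |

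The upper end approaches the 0.314 that the design is powered to detect.

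**4. Age alone.** AUC = Φ(δ/√2), which is 0.56, 0.58 and 0.64 for δ = 0.2, 0.3 and 0.5.

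**5. Whole classifier, age not entered.** Simulation: linear discriminant, 10-fold cross-validated AUC, 160 against 160, 8 features with ρ of 0.3-0.5 and no cannabis effect. The one-sided 5% critical AUC, from 2,000 data sets with no association, was 0.566-0.567. Ranges cover three separate runs of this kind:

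| Assumed age gap | Falsely significant |
|---|---|
| 0.2 SD | 10-16% |
| 0.3 SD | 17-32% |
| 0.5 SD | 46-78% |

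With features residualised on age, the rate was 3-7%. With no gap it is nominal by construction of the critical value.

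**6. Does listing age as an input cure this?** For accuracy, no. Mean AUC with 20 null features, a ridge linear classifier and 300 runs per setting (ranges over ρ = 0.3 and 0.5):

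| δ | Unadjusted | Age added as a feature | Residualised on age |
|---|---|---|---|
| 0 | 0.49 | 0.49 | 0.49 |
| 0.3 | 0.53-0.54 | 0.54 | 0.50 |
| 0.5 | 0.57-0.59 | 0.59 | 0.49 |

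The AUC with age added does not exceed what age alone would give (0.58 and 0.64 in step 4). A demographics-only reference model would therefore expose the problem.

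For the biomarker list, partly. With age forced into a joint linear model, null features reached p<0.05 in about 5% of cases at every gap, against 9-60% without it. With BIC forward selection and a 0.5 SD gap, at least one false feature was chosen in 64-93% of runs when age was not a candidate and in 14-18% when it was. The baseline with no imbalance was 10-11%. At 0.2-0.3 SD, 18-33% remained even with age as a candidate. So an optional candidate reduces false selection but does not remove it.

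**The case against.** The case on the other side has several sound parts.

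- **Raw inputs.** A reader might infer that the classifiers take raw volumes and raw scores with no demographic adjustment at all. The documents do not say so. Raw scores are named only for the 2a linear models, and section F allows for normative correction of some tests and for examining sex throughout. These provisions are partial: correction is optional, does not cover timed tests, and says nothing of volumes or immune markers.
- **1c is different.** Its stated features are immune markers, so the argument from volumes and test scores belongs to 2c. The gap in the text is the same for 1c, but its size there depends on how those markers vary with age and sex, which the documents do not give.
- **Demographics as inputs may be the intended route to conditioning.** The plan says selection will drop redundant biomarkers, and two cited methods, judging by their titles, use conditional or high-order mutual information. A marker informative only through age is redundant once age is in. This stands as a possibility, and it is a good reason not to remove demographics from the candidates. But the plan does not require it, and step 6 shows that optional entry is not enough.
- **Limited stakes.** 1c and 2c look for novel associations, while the formal group comparisons are 1a and 2a. That lowers the severity. It does not change the fact that the 1c and 2c output is worded as an effect.
- **Simplified simulation.** The plan's aim of separating HIV serostatus from cannabis use may involve more than two classes. The percentages are illustrations, not predictions.

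**Conclusion.** The concern holds in this form: for 1c and 2c no demographic adjustment is specified, no matching of users to non-users is stated, and the planned permutation test cannot tell a demographic signal from a cannabis effect. It is worth correcting before the classifiers are run.

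The size is unknown because it depends on the age gap. On the assumptions above, with age not entered as a feature, false significance is about 10-16% at 0.2 SD and 46-78% at 0.5 SD, and not above nominal with no imbalance. Only age was simulated; the argument for sex and WRAT-4 is the same in kind.

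A reader might also infer that users are in fact younger, or that the resulting list will be an artefact. The documents support neither. They show only that the plan would not detect this if it happened.

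**What to change.** In the SAP text for both 1c and 2c:

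1. Fit a reference classifier on age, sex and WRAT-4 only, in the same folds and repeats. Claim a cannabis signature only for the gain in AUC or log loss of demographics plus biomarkers over this reference.
2. Select and report biomarkers conditional on these demographics. Either force them into the model, or residualise each feature on them with coefficients estimated in the training folds only. For volumes in 2c, include head size.
3. Keep sex available as a predictor of interest, as section F intends. Do not simply remove demographics from the candidate set, since that would drop the plan's one possible route to conditioning.

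The demographics are already to be collected, so the cost is SAP wording and a few lines of code. The downside is that the incremental performance reported will be lower than an unadjusted AUC.

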Hypothesis 1c: Data driven classification models will reveal novel mechanisms and associations between regular cannabis use and peripheral and brain immune activity indices (e.g. CD4/CD8 ratio, sCD14, sCD163, MCP-1, neopterin, and monocyte subpopulations, and cellularity) that differentiate HIV serostatus from cannabis use.

C2 Secondary Aim

Specific Aim 2. Cannabis use impairs cognitive performance and brain structure in both PLWH/CB+ and CON/CB+.

Hypothesis 2a: Cognitive performance (particularly working memory and executive function) and brain volumetrics (temporal and parietal lobes) will be worse in regular cannabis users regardless of HIV status.

Hypothesis 2b: The effects of cannabis on brain integrity will be moderated by THC and CBD concentrations.

Hypothesis 2c: Data-driven classification models will reveal novel highly dimensional mechanisms and associations between cannabis use and brain integrity that differentiate HIV serostatus from cannabis use.

C3 Innovation and Rationale for the Selection of Outcome Measures

3. Innovation

C3.1 Quantitative evaluation of both peripheral and brain markers of immune activity and inflammation will improve our understanding of the effects of regular cannabis use in PLWH. We will evaluate the effects of regular cannabis use on validated plasma and CSF markers of immune health and inflammation. This proposal will be the first to simultaneously acquire extensive phenotype data from peripheral and brain markers of immune function (e.g., CD4/CD8 ratio, peripheral monocyte subsets, plasma sCD14, and sCD163 and CSF MCP-1 and neopterin), brain structure (volumetrics), brain inflammation (cellularity), and cognition (neuropsychological performance (NP) testing) in virally controlled PLWH on cART and HIV- controls. Immune responses will be examined with regards to duration, frequency, type, and amount of cannabis used.

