A total of 160 PLWH (80 regular cannabis users and 80 non-users) and 160 demographically similar healthy HIV- controls (80 regular cannabis users and 80 non-users) may undergo multimodal neuroimaging, immunophenotyping (including blood and cerebrospinal fluid), and neuropsychological testing to address the specific aims. PLWH may be recruited from WUSTL Infectious Disease (ID) Clinic, the AIDS Clinical Trial Unit (ACTU), Volunteers for Health, The Spot, other area providers and by hanging flyers at various places in the community. HIV- controls may be recruited from similar demographic communities as the PLWH, as well as Volunteers for Health and the surrounding community and social organizations.

D2 Subject Selection and Withdrawal

D2.1 Inclusion Criteria

(1) Participants must be 18–70 years old.

- (2) PLWH must have documented HIV infection for approximately 1 year, be on a cART regimen for approximately ≥ 3 months, and be virally well-controlled (< 200 copies/mL).
- (3) HIV- controls must have confirmed HIV- serostatus.
- (4) Participants must complete at least 9 years of education.
- (5) Participants must be able to provide informed consent.
- (6) Female participants must have a negative pregnancy test or written documentation of tubal ligation, hysterectomy, post-menopausal status, etc. and cannot be breastfeeding.
- (7) Participants should have no contraindications to an MRI scan.
- (8) Participants should be willing to have cannabis use history confirmed via clinical interview and urine analysis.
- (9) All inclusion criteria at PI discretion.

D2.2 Exclusion Criteria

- (1) History of neurological disorder (e.g., stroke, epilepsy, head injury with loss of consciousness for > 5 minutes, developmental learning disability, etc.).
- (2) Uncontrolled major affective disorder; any history of schizophrenia. Major depression or Bipolar disorder controlled with no hospitalizations and suicidal ideation in the past year is allowed.
- (3) Current substance use disorder (SUD) other than cannabis use disorder (CUD) and mild Alcohol Use Disorder as defined by DSM-5 criteria. A past SUD approximately > 1 year before the time of study enrolment may be allowed.
- (4) currently prescribed anti-coagulants (only exclusionary if participant will engage in optional LP).
- (5) an allergy to lidocaine or similar anesthetic (only exclusionary if participant will engage in optional LP).

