Aim 1: *Hypothesis 1a.* The effect of regular cannabis use on peripheral and brain inflammatory markers (primary response: composite markers; secondary: individual inflammatory markers) will be analyzed using linear models (analysis of covariance), including as predictors cannabis status, HIV, and their interaction. If an interaction effect between cannabis and HIV status is not significant, additive effects will be evaluated. Demographic factors such as Wide Range Achievement Test (WRAT)-4, sex, and age will be examined as explanatory variables and incorporated into the final models if significant at $p < 0.20$ on backward model selection. Secondary marker analyses will control for multiple tests by keeping the overall FDR at level $\alpha = 0.05$. The effect of cannabis on peripheral and brain inflammatory markers among PLWH and HIV- controls will be reported based on these models using a 95%CI. In the absence of a HIV-by-cannabis interaction, the additive effects of cannabis and HIV are of primary interest. If an interaction is present, then the primary comparison will be between CB+ and CB- groups among PLWH (at $\alpha = 0.05$). Secondary analyses will compare the PLWH, CB+ to the other two groups (at familywise error rate $\alpha = 0.05$).

Hypothesis 1b. The relationship between cannabis exposure (KMSK and urine analysis of cannabis metabolites) and peripheral and brain immune activity markers (primary response: composite markers; secondary: individual markers, possibly log-transformed, as noted above) will be analyzed among regular cannabis users using linear models. Demographic factors such as the WRAT-4, sex, and age will be examined as explanatory variables and incorporated into the final models if significant at $p < 0.20$ on backward model selection. In addition to linear effects, non-linear cannabis effects will also be considered, including quadratic effects and smooth effects fitted via generalized additive models. Possible interactive effects between cannabis exposure levels and HIV will also be examined.

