Hypothesis 1b. We have $\geq 80\%$ power to detect an association between cannabis exposure and peripheral immune activity markers explaining $R^2 = 0.047$ or more of the variance in the response, corresponding to a small Pearson correlation coefficient of $r = 0.219$ or higher. This effect size is achievable. In our preliminary data, we observed higher correlation levels (Figure 4). For brain inflammatory activity

markers the corresponding values are $R^2=0.069$, $r=0.262$. The power calculations used statistical software (G*Power).

Hypothesis 1c: Sample size determination for classifier development aims will seek to improve predictor accuracy and significance.⁹⁸ Sample size determinations were conducted using proposed published methods. Training and testing errors of cross validated progressively sampled models will be assumed to follow power laws and will be evaluated based on asymptotic error value convergence to identify appropriate sample sizes.^{99, 100} Results will be optimized based on nonlinear weighted least squares fitting.¹⁰¹ Cross validated model performance will be compared using empirical and uniform priors to determine the effect of balanced classes.¹⁰² Cross validation of data with randomly permuted labels will be used to identify the significance of model results.¹⁰³

Aim 2:

Hypothesis 2a: The effect of cannabis and HIV on cognition will be quantified through linear models, similar to those discussed under Hypothesis 1a, adjusting for confounding factors. The main NP outcomes of interest are raw scores from the working memory/executive function domain scores. Secondary outcomes are cognitive domain-specific scores and global deficit score, with FDR control, as discussed above. We expect to find additive but not interactive effects of HIV and cannabis use on primary NP outcomes. Separate analyses will examine the effect of cannabis on NP outcomes, controlling for peripheral immune indices.

Analyses of brain volumetrics will focus on the hippocampus as the primary outcome. Secondary outcomes will include the caudate, amygdala, putamen, and pre-frontal regions (with FDR corrections). These volumetric analyses will follow a similar pattern to that described for NP outcomes.

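### Aim 2 is worded as cannabis harm in both PLWH and HIV- users, but the Hypothesis 2a analysis tests and powers only the average effect

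*Combined protocol and SAP*

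**What the plan says.** Section C2 words Specific Aim 2 as "Cannabis use impairs cognitive performance and brain structure in both PLWH/CB+ and CON/CB"+ (the cannabis users in each HIV group). Hypothesis 2a beneath it says that working memory and executive function, and temporal and parietal volumes, "will be worse in regular cannabis users regardless of HIV status".

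Section F, Aim 2, Hypothesis 2a uses linear models similar to those of Hypothesis 1a. It names working memory/executive function and the hippocampus as main outcomes and adds: "We expect to find additive but not interactive effects of HIV and cannabis use on primary NP outcomes".

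The Hypothesis 1a text fits cannabis, HIV and their interaction, then says: "If an interaction effect between cannabis and HIV status is not significant, additive effects will be evaluated". If the interaction is significant, the primary comparison is users against non-users among PLWH, and the secondary ones compare PLWH users with the remaining two groups. The same paragraph promises the cannabis effect on inflammatory markers in PLWH and in HIV- controls with a 95% CI, but attaches no decision to it.

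The Power Analysis for Aim 2 claims, for n=320, at least 80% "statistical power to detect additive effects of HIV status and cannabis use on NP and volumetrics outcomes corresponding to Cohen's $d=0.314$ each". It sets beside this preliminary values of 0.584 for cannabis and 0.418 for HIV.

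**The concern.** Harm in both strata is a statement about two effects. It is false if either one is zero. The pooled additive term concerns one quantity, the mean of the two effects, and can be clearly non-zero when only one stratum is affected. The only step from the average to *both* is a non-significant interaction, for which the plan gives no margin or bound. Because additivity is announced as the expected finding, a non-significant interaction is easily taken as confirming it.

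If the 1a branching carries over, users against non-users among HIV- controls, which is half of the Aim 2 sentence, is not a named test on either route. Under the additive model the cannabis estimate is the same in both HIV groups by construction, so data from one group can supply the result for the other.

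Section B1.8 hopes the results will inform cannabis policy and clinic recommendations for PLWH, so it matters which population the evidence supports.

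**Working it through.** **Inputs.** Four cells of 80 (Section D1: "160 PLWH (80 regular cannabis users and 80 non-users) and 160 demographically similar healthy HIV- controls (80 regular cannabis users and 80 non-users"). Two-sided 0.05 (Section F: "All statistical tests will be two-sided, with significance declared at the $p < 0.05$ level (unless otherwise stated"). d=0.314, 0.584 and 0.446 from the power paragraphs of Section F. SD is set to 1, with no covariates and no missing data. The documents give no stratum-specific effects for Aim 2, so effects confined to one stratum are an assumption, shown over a range.

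**1. The plan's own figure.** Pooled, 160 v 160: SE = sqrt(2/160) = 0.1118. At d=0.314 a two-sample t test has power 79.96% (80.2% by normal approximation). The figure reproduces as a pooled main-effect test. For one stratum, 80 v 80: SE = sqrt(2/80) = 0.1581, and d=0.446 gives 80.1%, matching the PLWH-only figure in the Aim 1 power text.

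**2. Power to show harm in each stratum.** The strata are independent, so joint power is the product of two 80 v 80 powers.

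| d in each stratum | One stratum | Both |
|---|---|---|
| 0.314 | 50.6% | 25.6% |
| 0.446 | 80.1% | 64.1% |
| 0.511 | 89.5% | 80.1% |
| 0.584 | 95.6% | 91.5% |

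Joint power of 80% needs sqrt(0.80) = 89.4% in each stratum, hence about d=0.51. At d=0.314 it would need about 211 per cell, 844 in all.

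**3. Effect d in one stratum, zero in the other.** The interaction contrast has expectation d and SE sqrt(4/80) = 0.2236, so its ratio is d/0.2236. The pooled effect has expectation d/2 and SE 0.1118, which is the same ratio. The two contrasts are orthogonal, so with p = Φ(d/0.2236 − 1.96), the chance of a non-significant interaction together with a significant harmful pooled effect is close to (1 − p) × p. This cannot exceed 25%.

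| d in the affected stratum | p | (1 − p) × p |
|---|---|---|
| 0.3 | 0.268 | 19.6% |
| 0.4 | 0.432 | 24.5% |
| 0.446 | 0.514 | 25.0% |
| 0.5 | 0.609 | 23.8% |
| 0.584 | 0.743 | 19.1% |

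Simulation of the sequence agrees: 24.9% at 0.446 and 19.2% at 0.584 (2,000,000 replicates). Requiring significant harm in each stratum holds the same event to 2.5% or less.

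**4. How much a non-significant interaction rules out.** The 95% CI half-width for the interaction is 1.967 × 0.2236 = 0.44 SD. A true 0.5-SD difference between strata is missed 39% of the time (1 − 0.609).

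**The case against.** Several points on the other side stand.

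- **No written decision rule.** A reader might infer that the plan will report a significant pooled effect as harm in both strata. No sentence says so, and the Aim 2 line can be read as a statement of expectation. The 19% to 25% is therefore conditional on that reading and is not an error rate of the plan as written.
- **The power statement is correctly labelled.** A reader might infer that d=0.314 overstates the power. It does not: it names additive effects and reproduces for them. What is absent is a figure for the stronger wording.
- **Hypothesis, model and power can be read consistently.** The Hypothesis 2a wording is ordinary main-effect language, and additive effects are what is modelled and powered. Only the Aim 2 sentence says *both*.
- **Stratum estimates may already be intended.** The Hypothesis 1a sentence on 95% CIs by HIV group may carry over, and separate reporting makes most sense from the interaction model. It is nevertheless written for inflammatory markers and does not say which model applies.
- **The scenario is extreme.** It sets one effect at exactly zero. Section B1.7 describes consistently smaller hippocampi in HIV- regular users, which weighs against a PLWH-only effect on that outcome. Cognitive findings in PLWH are mixed (Section B1.6), so the reverse case stays open.
- **Requiring significance in each stratum is costly.** With a true d=0.314 in both, it misses the correct conclusion about 74% of the time. About half of such trials would show exactly one significant stratum (2 × 0.506 × 0.494), inviting a spurious contrast between groups. If effects are additive, the pooled test is the efficient one.

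The gap between the Aim 2 sentence and the test remains after all of this.

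**Conclusion.** The concern holds in limited form. The analysis named for Hypothesis 2a supports a conclusion about the average cannabis effect across HIV strata. It does not by itself support harm in both, and the HIV- comparison is not named in either branch, taking the 1a rules to apply to 2a as the word similar suggests.

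The d=0.314 figure is right for what it names. For the *both* wording, power is about 26% at that effect in each stratum and about 91% at 0.584 in each, so the gap matters mostly for effects nearer 0.314. The preliminary 0.584 is not given by stratum, so its application to each is an assumption. Missing cognitive or MRI data would lower all these powers.

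The documents do not support calling the power calculation wrong, nor treating a two-stratum significance rule as the only acceptable remedy. This is a mismatch in a secondary aim that can be settled in the text, and it is worth settling before analysis.

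**What to change.** In Section F, Hypothesis 2a, for the primary cognitive outcome and hippocampal volume:

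1. Pre-specify users minus non-users within PLWH and within HIV- controls, each with a 95% CI, from the cannabis-by-HIV model whether or not the interaction is significant.
2. Report the interaction with its 95% CI. Do not infer harm in both strata, or absence of interaction, from a non-significant result.
3. Keep the pooled effect as the powered test of the average cannabis effect.
4. Choose the wording of the Aim 2 conclusion: either an average effect across HIV strata, or *both* reserved for significant harm in each stratum. In the second case each test can be at two-sided 0.05 with no further adjustment, since both must succeed.
5. Add to the Power Analysis for Aim 2 that d=0.314 is for the pooled average, d=0.446 for one stratum, and about d=0.51 in each for a claim about both.

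The cost is a few sentences and two contrasts from a model already planned, with no new participants or data. The price of keeping *both* is lower power: the detectable effect rises from 0.314 to about 0.51, still below the preliminary 0.584. Limiting the conclusion to the average effect avoids that price.
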